12.5 Electronic Case Report Forms

All study data must be incorporated in the corresponding eCRFs which are designed for computer processing and analysis. The Investigator will be responsible for recording all data in the eCRFs and must ensure the accuracy, completeness, legibility, and timeliness of the data reported to the Sponsor in the eCRF and in all required reports.

Data from clinical laboratory reports, etc, will be incorporated into the eCRFs either by direct transcription into appropriate eCRF pages or by inclusion of photocopies of these reports with printouts of the appropriate eCRF pages and stored in the site's Study Binder.

If corrections are made following official final review and sign-off by the Investigator, the Investigator must be made aware of the changes and provide written acknowledgement.

This study will be conducted in compliance with the regulations contained within 21 CFR Part 11, electronic records/electronic signatures regulations.

12.6 Retention of Study Records

GCP regulations require that the Investigator retain all documentation related to this clinical trial for a period of 2 years after the approval of the NDA in the US (or Product License outside the US) for this drug or 2 years after the withdrawal of the IND. These records include the protocol and copies of all documents submitted to the Sponsor or to government authorities, subject records (including signed ICFs, subject charts, eCRFs, and other source documents), IRB/EC approvals and correspondence, records of drug accountability, and all study communications, whether written, telephonic, or electronic. None of the required documents will be destroyed or transferred to the control of another party without the written approval of the Sponsor.

If the Investigator cannot guarantee the archiving requirement at the site for any or all of the documents, special arrangements must be made between the Investigator and the Sponsor to store these in a sealed container outside of the study site so that they can be returned sealed to the Investigator in case of a regulatory audit. When source documents are required for the continued care of the subject, appropriate copies will be made for storing outside of the study site.

12.7 Monitoring the Study and Data Quality Assurance

Representatives of the Sponsor (or designees) will contact the Investigator and his/her staff prior to the start of the trial to review the procedures to be followed in conducting the study and recording the findings, and to confirm the facility's readiness to conduct the trial.

It will be the monitor's responsibility to inspect the eCRFs at regular intervals throughout the study, to verify the adherence to the protocol and the completeness, consistency, and accuracy of the data being entered on them. The monitor must have access to all study related reports and

records needed to verify the entries on the eCRF. The Investigator (or designee) must agree to cooperate with the monitor to ensure that any problems detected in the course of these monitoring visits are resolved and agree to provide missing information and grant access to all study documentation.

Every attempt must be made to follow the protocol, obtain and record all data requested for each subject at the specified times. However, ethical reasons may warrant the failure to obtain and record certain data or to record data at the times specified. If data is not recorded per protocol, the reasons must be clearly documented on the eCRF/records.

Accurate and reliable data collection will be ensured by the verification of the eCRFs against the Investigator's records by the monitor (source documentation verification). Collected data will be entered into a computer database and subject to electronic and manual quality assurance procedures.

The study data must be verifiable with the source data, which requires access to all original recordings, laboratory reports, product accountability records, including access to the subject electronic medical record, and source data must be made available for all study data. Subjects must also allow access to their medical records. They will be informed of this and must consent to permission by providing their signature on the ICF prior to enrollment.

Representatives of the Sponsor (or designees) may audit the study periodically to ensure that all records are correct and complete. The verification of the eCRF data must be by direct inspection of source documents.

12.8 Discontinuation of the Study

The Sponsor reserves the right to discontinue this study for administrative reasons at any time.

The trial may also be terminated prematurely if unexpected AEs occur or if the Investigator does not adhere to the protocol.

12.9 Policy for Publications

The detailed procedures for the review of publications are set out in the clinical trial agreement entered into with the Sponsor in connection with this study. Results from the study shall not be made available to any third party by the Investigator or staff outside of the publication policy.

13 ETHICS

13.1 Ethics Review

The final study protocol, including the final version of the ICF, must be approved or given a favorable opinion in writing by an IRB/EC as appropriate. The IB may also be provided as required. The Investigator must submit written approval from an IRB/EC to the Sponsor or a designee such as a Contract Research Organization (CRO) before the Investigator may initiate this study.

The Principal Investigator is responsible for informing the IRB/EC of any amendment to the protocol in accordance with local requirements. In addition, the IRB/EC must approve all advertising used to recruit subjects for the study. The protocol must be re-approved by the IRB/EC upon receipt of amendments and annually, as local regulations require.

The Principal Investigator is also responsible for providing the IRB with reports of any reportable serious adverse drug reactions from any other study conducted with the investigational product. The Sponsor or the CRO will provide this information to the Principal Investigator.

Progress reports and notifications of serious adverse drug reactions will be provided to the IRB/EC according to local regulations and guidelines.

13.2 Ethical Conduct of the Study

The study will be performed in accordance with ethical principles that have their origin in the Declaration of Helsinki and are consistent with ICH/Good Clinical Practice and applicable regulatory requirements.

13.3 Written Informed Consent

A properly executed, written informed consent document, in compliance with 21 CFR 50, the ICH guidelines, and relevant local regulatory requirements, will be obtained from each subject before the subject is enrolled into the study and before any study-related procedure is performed. Attention will be directed to the basic elements required for incorporation into the informed consent under US Federal Regulations for Protection of Human Subjects (21 CFR 50.25[a]) and (21 CFR 50.25[b]).

The informed consent document will be reviewed by the Sponsor or designee for inclusion of all required elements prior to submission to the IRB/EC. The Sponsor must also review any revisions to the approved informed consent document prior to submission to the IRB/EC. The final IRB/EC-approved document must be provided to the Sponsor for regulatory purposes. It is the responsibility of the Investigator, or a person designated by the Investigator, to obtain written informed consent from each subject (or the subject's legally authorized representative) participating in the study after adequate explanation of the aims, methods, anticipated benefits, and potential hazards of the study. In the case where the subject is unable to read the form, an impartial witness will be present during the entire informed consent discussion. After the subject has orally consented to participate in the study, the witness' signature on the form will attest that the information in the consent form was accurately explained and understood.

A copy of the fully executed informed consent document must be provided to the subject or the subject's legally authorized representative. If applicable, it will be provided in a certified translation of the local language by the site under the guidance of the Investigator. Signed informed consent documents must remain in each subject's medical record and be made available for verification by the monitor at any time.

If new safety information results in significant changes in the risk/benefit assessment, the consent form will be reviewed and updated as necessary. All subjects (including those who have already been treated with Yutiq 0.05 mg) will be informed of the new information and given a copy of the revised form to provide their consent in order to continue participation in the study.

APPENDIX 1: Measurement of BCVA by ETDRS

The procedure for carrying out the testing of best-corrected visual acuity (BCVA) measured according to the standard procedure originally developed for Early Treatment Diabetic Retinopathy Study (ETDRS) will be covered in a separate document with instructions provided by the independent certification vendor selected by the Sponsor.

APPENDIX 2: Slit Lamp Biomicroscopy, Ophthalmoscopy, and Intraocular Pressure

Slit Lamp Examination

A routine slit lamp examination will collect clinical findings from the anterior and posterior segment of both study and fellow eye and should be conducted after IOP measurement has been completed.

[figure not shown]
Anterior Chamber Cell Grading Scale

Anterior chamber cells will be measured using a Haag/Streit or similar slit lamp at high magnification (1.6 X) 1-mm beam. The same instrument, and when possible, the same examiner should be used on each patient throughout the study. Assessment will be made using the following scale (Jabs et al. 2005).

Field size: 1 mm by 1 mm slit beam

0	<1 cells/hpf
0.5+	1-5 cells/hpf
1+	6-15 cells/hpf
2+	16-25 cells/hpf
3+	26-50 cells/hpf
4+	>50 cells/hpf

Anterior Chamber Cell Scoring Convention

Anterior chamber cells: \geq 2 step increase															

The diagram on the right presents the scoring convention that will be used to identify a minimum of "\geq 2 step increase" of anterior chamber cells for the primary efficacy endpoint.
  

Score *	Cell Count*	

0	<1 cells/hpf	

0.5+	1-5 cells/hpf	

1+	6-15 cells/hpf	

2+	16-25 cells/hpf	

3+	26-50 cells/hpf	

4+	>50 cells/hpf	

 
* Jabs et al 2005
	Score *	Cell Count*	0	<1 cells/hpf	0.5+	1-5 cells/hpf	1+	6-15 cells/hpf	2+	16-25 cells/hpf	3+	26-50 cells/hpf	4+	>50 cells/hpf	
Score *	Cell Count*														
0	<1 cells/hpf														
0.5+	1-5 cells/hpf														
1+	6-15 cells/hpf														
2+	16-25 cells/hpf														
3+	26-50 cells/hpf														
4+	>50 cells/hpf														

Ophthalmoscopy

[figure not shown]
Ophthalmoscopy will be performed to assess retinal and choroid appearances and vitreous haze ([Nussenblatt et al. 1985](#)). Indirect ophthalmoscopy will be performed for study eye and fellow eye with pupil dilation and should be conducted after IOP measurement has been completed.

Vitreous Haze Grading Scale

The following scale will be used to define the extent of vitreous haze:

Absent	Clear view of optic disc, retinal vessels and nerve fiber layer
Trace	Slight blurring of optic disc margin and of normal striations and reflex of nerve fiber layer
1+	Mild blurring of optic disc margin and slight loss of retinal vessel definition
2+	Moderate blurring of optic disc margin and loss of retinal vessel definition
3+	Optic nerve head and large vessels visible but borders quite (very) blurry
4+	Optic nerve head obscured

Vitreous Haze Scoring Convention

Vitreous Haze: \geq 2 step increase															
The diagram on the right presents the scoring convention that will be used to identify a minimum of " \geq 2 step increase" of vitreous haze for the primary efficacy endpoint.	 

Score*	Characteristics*	

Absent [0]	Clear view of optic disc, retinal vessels and nerve fiber layer	

Trace [0.5]	Slight blurring of optic disc margin and of normal striations and reflex of nerve fiber layer	

1+	Mild blurring of optic disc margin and slight loss of retinal vessel definition	

2+	Moderate blurring of optic disc margin and loss of retinal vessel definition	

3+	Optic nerve head and large vessels visible but borders quite (very) blurry	

4+	Optic nerve head obscured	

 
* Nussenblatt et al 1985
	Score*	Characteristics*	Absent [0]	Clear view of optic disc, retinal vessels and nerve fiber layer	Trace [0.5]	Slight blurring of optic disc margin and of normal striations and reflex of nerve fiber layer	1+	Mild blurring of optic disc margin and slight loss of retinal vessel definition	2+	Moderate blurring of optic disc margin and loss of retinal vessel definition	3+	Optic nerve head and large vessels visible but borders quite (very) blurry	4+	Optic nerve head obscured
Score*	Characteristics*														
Absent [0]	Clear view of optic disc, retinal vessels and nerve fiber layer														
Trace [0.5]	Slight blurring of optic disc margin and of normal striations and reflex of nerve fiber layer														
1+	Mild blurring of optic disc margin and slight loss of retinal vessel definition														
2+	Moderate blurring of optic disc margin and loss of retinal vessel definition														
3+	Optic nerve head and large vessels visible but borders quite (very) blurry														
4+	Optic nerve head obscured														

Fundus Examination

The fundus assessments should be conducted using indirect ophthalmoscopy with a 20 diopter, 28 diopter, or 30 diopter condensing lens. In order to minimize variability, every effort should be made to have a single examiner conduct all assessments on a given subject.

Intraocular Pressure

Intraocular pressure will be assessed by applanation tonometry (preferably, Goldmann) and should be measured only after slit lamp examination has been completed. The mean of 3 measurements per eye will be recorded as the IOP. All reasonable efforts should be made to have the same examiner obtain all IOP measurement for a given subject. Measurement should be performed before dilated ophthalmoscopy.

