7.6 Rescue Treatment of Recurrence of Uveitis

In the event of a uveitis recurrence in either eye (defined as an “Endpoint”), peri-ocular or intraocular corticosteroid injections, or topical medications should be administered as first line local therapy, in accordance with the protocol. Investigators should consider treatment with topical steroids as first line therapy for a recurrence that involves only an increase in anterior chamber cells with no increase in vitreous opacity. Systemic immunosuppressants or systemic steroids should be used only if local therapy fails.

Subjects who experience a recurrence of uveitis will continue participation in the study. Once the subject’s recurrence is controlled, the treatment regimen (local or systemic therapy) will be ended in a manner that follows the standard of care for ending the specific treatment regimen.

Details of each recurrence and its treatment will be documented in the eCRF.

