7.7 Prohibited Medications

Other than the exceptions described in [Section 7.2](#), [Section 7.6](#), or below, the following concomitant medications are not permitted during the study:

- Oral, systemic, injectable, or topical steroids
- Systemic immunosuppressants

Systemic medications or topical steroids administered as part of gradual dose reduction (tapering), as described in [Section 7.2](#), are not considered prohibited medications. Additionally, topical steroids administered as short-term standard treatment following an ocular surgical procedure are not considered prohibited medications.

It is advisable for the Investigator to discuss treatment with the Medical Monitor before administering any prohibited medication unless it is an emergency.

Any medications or therapies that the subject is using during the study period and that would preclude eligibility as indicated in the Exclusion Criteria ([Section 4.2](#)), are prohibited medications.

All prohibited medications used concurrently (from Day 1 through Month 12) must be documented in the eCRF.

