10 ASSESSMENT OF EFFICACY

10.1 Primary Efficacy Endpoint

The primary efficacy endpoint will be the proportion of subjects who have a recurrence of uveitis in the study eye within 24 weeks (6 months) after receiving study treatment. Recurrence is defined as:

- An increase in the vitreous haze of ≥ 2 steps compared to baseline or any visit time point prior to the Week 24 visit;

OR

- A deterioration in visual acuity of at least 15 letters BCVA compared to baseline or any visit time point prior to the Week 24 visit.

Any criterion used to define recurrence must be attributable only to noninfectious uveitis. To prevent post-procedural inflammatory reactions from being reported as uveitis recurrences, assessments for recurrence of uveitis begin after the Study Day 7 visit.

Refer to [Appendix 2](#) for additional information.

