4.2. Primary Efficacy Endpoint Analysis

4.2.1. Definition of Endpoint

The primary efficacy endpoint is the proportion of subjects who have a recurrence of uveitis in the study eye within 24 weeks (6 months) after receiving study treatment. Recurrence is defined as:

- An increase in the vitreous haze of ≥ 2 steps compared to baseline at the Week 24 visit, or any visit time point prior to the Week 24 visit after the Study Day 7 visit

Or

- A deterioration in visual acuity of at least 15 letters BCVA compared to baseline at the Week 24 visit, or any visit time point prior to the Week 24 visit after the Study Day 7 visit.

Any criterion used to define recurrence must be attributable only to noninfectious uveitis. To prevent post-procedural inflammatory reactions from being reported as uveitis recurrences, assessments for recurrence of uveitis begin after the Study Day 7 visit.

The study protocol stated to impute subjects who don't complete Week 24 eye examinations and subjects who take prohibited medications as having a recurrence. Consider the fact that the study was terminated early, no imputation will be implemented. Summary of the primary efficacy endpoint will be based only on the observed data from the subjects who reached Week 24.

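### Protocol Appendix 2 assigns an anterior chamber cell rise to the primary endpoint, Section 10.1 and the SAP do not, and the SAP's recurrence rate will not show flares treated below its thresholds

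*Protocol*

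**What the plan says.** Protocol 10.1 gives two alternative components of recurrence in the study eye. One begins "An increase in the vitreous haze of" at least 2 steps; the other is "A deterioration in visual acuity of at least 15 letters BCVA compared to baseline" or another visit before Week 24. Anterior chamber cells are not listed. The section then sends the reader to Appendix 2.

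Appendix 2 has two parallel scoring boxes, one for haze and one for cells. The cell box says a rise of at least 2 steps is identified "of anterior chamber cells for the primary efficacy endpoint".

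Protocol 7.6 opens "In the event of a uveitis recurrence in either eye (defined as an “Endpoint" and goes on to advise on treatment "for a recurrence that involves only an increase in anterior chamber cells with no increase in vitreous opacity". It asks that each recurrence and its treatment be recorded in the eCRF.

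Protocol 10.2 places cells elsewhere, in a secondary endpoint of iridocyclitis recurrence with a threshold of more than 2 steps.

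SAP 4.2.1 keeps haze and BCVA ("A deterioration in visual acuity of at least 15 letters BCVA compared to baseline at the Week 24 visit", or at an earlier visit after Day 7) and lists no cell criterion. It sets aside the protocol's imputed recurrences: "Consider the fact that the study was terminated early, no imputation will be implemented". The summary is limited to observed data from subjects who reached Week 24. SAP 4.2.3 plans no sensitivity analysis. SAP 4.4.5.1 tabulates cell rises of at least 2 steps under safety.

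**The concern.** A site following Section 10.1 to Appendix 2 finds cells and haze described in the same way for the same endpoint, and Section 7.6 uses the word recurrence for an event that involves cells alone. Such events may therefore have been logged and treated as recurrences. The SAP does not say whether recurrence is taken from the graded values or from the site's recurrence record, and SAP 4.3.1.3 counts recurrences on the same basis.

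At stake is what the reported rate means. If steroid treatment in the study eye stops a flare before haze rises 2 steps or vision falls 15 letters, the subject enters the summary as recurrence-free. A reader who takes the rate as freedom from inflammation or treatment would be misled. The protocol's iridocyclitis endpoint and its count of adjunctive treatments, which would have shown such flares within efficacy, are not in the SAP's reduced list (SAP 1.1).

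**Working it through.** The documents state no expected recurrence rate, effect size or power, so there is no figure to reproduce. The check compares texts and then sizes the effect under stated assumptions.

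**1. Criteria side by side**

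| Place | Haze | BCVA | Anterior chamber cells |
|---|---|---|---|
| Protocol synopsis (primary endpoint), 10.1 | ≥2 steps | ≥15 letters | not listed |
| Protocol Appendix 2 | ≥2 steps, primary endpoint | no threshold | ≥2 steps, primary endpoint |
| Protocol 7.6 | no threshold | no threshold | cell-only recurrence, no threshold |
| Protocol 10.2 (also in synopsis) | – | – | >2 steps, secondary endpoint |
| SAP 4.2.1 | ≥2 steps | ≥15 letters | not listed |
| SAP 4.4.5.1 | – | – | ≥2 steps, safety; not tied to the primary endpoint |

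**2. Who falls between the definitions**

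Inclusion criterion 4 requires fewer than 10 cells/HPF in the study eye on Day 1. On the Appendix 2 scale this allows grades 0, 0.5+ and 1+ (6–15 cells). Taking one step as one adjacent grade (an assumption, since the diagram is not available):

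| Baseline | ≥2 steps reached at | >2 steps reached at |
|---|---|---|
| 0 | 1+ | 2+ |
| 0.5+ | 2+ | 3+ |
| 1+ | 3+ | 4+ |

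A subject who goes from 0 to 1+, without a 2-step haze rise or a 15-letter loss, meets the Appendix 2 convention. The same subject has no recurrence under 10.1 or SAP 4.2.1 and does not meet the 10.2 iridocyclitis threshold.

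**3. What happens if that flare is treated**

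- Protocol, topical steroid or other rescue accepted under 7.6: Section 7.7 exempts 7.6 rescue from the prohibited list, and 11.4.4 says topical steroids are not treated as prohibited. No recurrence is imputed.
- Protocol, non-topical treatment classed as prohibited in the Section 11.4.5 review: 11.4.4 imputes a recurrence. That class could turn on whether a cell-only flare is a recurrence, which is the point on which the texts differ.
- SAP: nothing is imputed in either case. The subject is recurrence-free unless haze or BCVA crosses its threshold.

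**4. Size**

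One reclassified subject among n changes the observed proportion by 1/n. The actual number reaching Week 24 is not given, so these denominators are assumptions; 30 is the planned arm size before enrollment stopped.

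- n = 10: 1/10 = 10.0 points
- n = 15: 1/15 = 6.7 points
- n = 30: 1/30 = 3.3 points

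With n = 30, x recurrences by haze or BCVA and a further subjects with a cell-only flare, the rate is (x + a)/30. The 95% limits are Clopper-Pearson, as in SAP 4.2.2. All counts are assumed.

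| x | a = 0 | a = 1 | a = 3 | a = 6 |
|---|---|---|---|---|
| 6 | 20.0% (7.7–38.6) | 23.3% (9.9–42.3) | 30.0% (14.7–49.4) | 40.0% (22.7–59.4) |
| 9 | 30.0% (14.7–49.4) | 33.3% (17.3–52.8) | 40.0% (22.7–59.4) | 50.0% (31.3–68.7) |
| 12 | 40.0% (22.7–59.4) | 43.3% (25.5–62.6) | 50.0% (31.3–68.7) | 60.0% (40.6–77.3) |

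**The case against.** The strongest reply is that the SAP has already settled the matter. SAP 4.2.1 is unambiguous, and SAP 4.4.5.1 reuses the cell-scoring text under safety without tying it to the primary endpoint. Cell rises, rescue and prohibited medication (SAP 4.4.7.1), the separate haze and BCVA proportions (SAP 4.2.2) and by-subject listings are all planned. The SAP's scope was reduced on purpose after early termination. It is dated 8 May 2023, about a year after enrollment stopped, so correcting site-facing text would now change little in conduct. This stands, and it limits the weight of the point. It does not remove the conflict within the protocol, and none of the planned tables joins cell rises or treatment to recurrence at the subject level.

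A reader might also infer two things that the documents do not support:

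- That Section 7.6 makes a cell rise a primary-endpoint event. It says Endpoint, without primary, applies to either eye and gives no step threshold; it can be read with the iridocyclitis and fellow-eye secondary endpoints. Only Appendix 2 names the primary endpoint.
- That dropping the imputation is what turns rescued cell-only flares into non-recurrences. For topical or Section 7.6 rescue the protocol would not have imputed one either. The SAP changes the result only for treatment classed as prohibited.

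**Conclusion.** The inconsistency is real and stands in current text: Appendix 2 against the synopsis, Section 10.1 and SAP 4.2.1, with Section 7.6 adding to the ambiguity, and more than 2 against at least 2 cell steps. The SAP's own definition is clear. The remaining weakness is one of interpretation: the descriptive rate may look lower than the rate of active or treated inflammation, and no planned analysis shows by how much.

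Each affected subject is worth 1/n, which is 3.3 to 10.0 points over assumed denominators of 30 down to 10. The number of such subjects is unknown and may be zero. A flare that also meets the haze or BCVA criterion is still counted.

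It would be too strong to say that the recurrence rate is understated: against the definition in Section 10.1 and SAP 4.2.1 it is not, because cell-only flares are outside that definition. Nor do the documents support a claim of bias between arms. Sham subjects were discontinued in early May 2022, only those who reached Week 24 are summarised, and no test is planned, so the point bears mainly on how the Yutiq 0.05 mg rate is read. This is a cheap improvement to make, not a flaw that invalidates the analysis.

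**What to change.** 1. Reconcile Appendix 2, Section 7.6 and Section 10.1, and the cell-step thresholds in Section 10.2, Appendix 2 and SAP 4.4.5.1. This review does not say which rule is right. At this stage the reconciliation can be stated in the SAP or the clinical study report.
2. In SAP 4.2.2, state that recurrence is derived from the recorded haze and BCVA values together with the required attribution to noninfectious uveitis, and say where that attribution is recorded. Values alone would drop a condition that both documents impose.
3. Add one supportive row beside the primary summary, on the same denominator and with the Clopper-Pearson interval. Count a subject with any of these by Week 24: the haze criterion, the BCVA criterion, a cell increase of at least 2 steps, rescue or prohibited treatment in the study eye, or prohibited systemic treatment.

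The cost is a few lines of text and one table row from data already collected for SAP 4.4.5.1 and 4.4.7.1. The downside for the sponsor is that the supportive rate cannot be lower than the primary one and may look less favourable.
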